3.1 Inclusion Criteria

- 3.1.1 Patients must be 18 years or older, but there is no upper limit on age of inclusion.
- 3.1.2 Patients must have a peripheral lung tumor that is amenable to SBRT as determined by the treating radiation oncologist. To be classified as a peripheral lung tumor, the tumor edge (the edge of the gross tumor volume or GTV in radiation treatment planning software) must be within 2 cm of the chest wall. This is determined by the treating radiation oncologist. The chest wall is defined as the chest wall musculature or ribs/vertebrae immediately adjacent to the lungs.
- 3.1.3 Patients must have ECOG status of 0-3
- 3.1.4 Patients must have a life expectancy of at least 3 months as determined by the treating radiation oncologist.
- 3.1.5 Patients must have the ability to understand and the willingness to sign an IRB-approved informed consent document.

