6.4 Duration of Follow-up

Follow-up for serious adverse events and mortality after the single dose of 150 mg of risedronate or placebo is administered will take place during the routine clinic visits during radiation treatment. Radiation treatments will occur within 1 – 3 weeks of taking the study drug. The 30 day follow-up window that is part of mandatory DSMC-SAE reporting will be considered 30 days from the end of all treatments of radiation. This visit can be either a phone call or a visit in person to review adverse events and may be conducted and documented in the medical record by either research study staff RNs or the treating physician. A window of +/- 7 business days is allowed for the 30 day followup assessment.

Specific toxicity related to radiation pneumonitis, radiation fibrosis, and chest wall pain will be collected at each followup point as per appendices K – M.

Patients removed from study for unacceptable adverse events will be followed until resolution or stabilization of the adverse event.

Patients will be followed for a minimum of 3 months for assessment of the primary objective.

Patients will be ideally followed in total for 12 months after completion of radiation therapy for the purposes of this study.

In the event that patients develop progressive disease or a new cancer, requiring additional chemotherapy they will be withdrawn from further study directed followup. In these situations, the followup schedules and imaging become dramatically different from what is directed on this protocol. Additionally further systemic chemotherapy treatments can heavily alter bone density/cortical thickness. As such, if patients develop new disease requiring additional systemic chemotherapy treatment outside of their initial SBRT, they will be withdrawn from study for further follow ups/study directed imaging. Any data that was collected prior to study withdrawal will still be used in analysis. **Immunotherapy or**

hormonal therapy for breast or prostate cancer will not be considered reasons for withdrawal.
Cryoablation or radiofrequency ablation will not be considered a reason for withdrawal from study.

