6.6 Study Calendar

	Baseline Prior to SBRT	Dosing (7- 21 days before SBRT)	During SBRT	1 month Post SBRT	3 ^f months post SBRT	6 ^f months Post SBRT	9 ^f months Post SBRT	12 ^f months Post SBRT
Informed consent	X							
Demographics Medical history History of diabetes Physical exam Performance status Vital signs Height, Weight, M ²		X						
Current Medications list	X				X			
Current or prior use of rank ligand inhibitors, bisphosphonates, and steroids with dates of use and dose as per Appendix G. ^h	X				X	X	X	X
CT chest with or without contrast	X ^a				X	X	X	X
Risedronate or placebo		X ^c						
Urine sample ^d	X				X	X	X	X
Serum Calcium EGFR Serum Creatinine Pregnancy test ^b		X						
Adverse event evaluation (Appendix E)					X			
Specific Radiation Related Chest wall Toxicity (Appendix K)				X ^e	X	X	X	X
Follow up phone call for assessment of adverse events without imaging (Appendix F)				X				
Fracture Incidence (Appendix Q)	X				X	X	X	X
Radiation Treatment Details (Appendix N)			X ^g					

^a Pre-SBRT CT chest scan will be the treatment planning scan. Fracture incidence will be assessed on CT scans

^b Urine pregnancy test (women of childbearing potential) performed within 1 week of treatment planning simulation for radiation.

^c Given once at 7 – 21 days prior to initiation of SBRT

^d For urine sample pick-up and transport, call [name] at [contact] (mobile), [contact] (office). If not available, call [name] at [contact] (mobile).

^e At the 30-Day time point this can be collected over the phone

^f Every 3 month follow-up, and CT imaging will have a window of +/- 8 wks

^g Appendix N may be completed during SBRT but should be completed within 12 weeks of completing SBRT

All pre-study activities must be completed within 12 weeks of the start of study drug including labs

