7.3 Detection of Rib/Vertebral Body fractures

The incidence of rib and or vertebral fractures within the radiation treatment field within the 50% isodose line will be collected from standard follow-up CT imaging at 3, 6, 9, and 12 months post SBRT.

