11.2 Analysis of Secondary Objectives

11.2.1

Percent change in cortical thickness across all time points

The percent change in mean cortical thicknesses from baseline will be assessed at 3 months, 6 months, 9 months, and 12 months post SBRT separately within regions of bone receiving 0 – 10 Gy, >10 – 20 Gy, > 30 – 40 Gy, and >40Gy. These outcomes will be compared using repeated measures analysis of variance (ANOVA).

11.2.2

Incidence and grade of chest wall pain

The incidence and grade of chest wall pain occurring inside the 50% isodose line will be collected and reported per modified CTCAE v5.0 (Appendix K) at 3 months, 6 months, 9 months, and 12 months post SBRT for all patients. Results will be compared between patients receiving placebo or risedronate. The incidence of G3 or greater chest wall pain will also be correlated with the volume of chest wall receiving at least 30 Gy or greater. The chest wall contour is defined as a 2 cm expansion from lung, from the costovertebral angle to the sternum.

11.2.3

Incidence of rib or vertebral fractures

The incidence of rib or vertebral fractures within the treatment field occurring at any time during the entire course of the study (12 months), will be reported and compared between patients receiving placebo or risedronate.

11.2.4

Urinary excretion of N-telopeptide (NTX)

The concentration of urinary NTX will be assessed at each time point from baseline to the conclusion of the study at 12 months. Results will be directly compared in each group.

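### The 12-month fracture comparison is a simple incidence with no rule for unequal follow-up; a censored cumulative incidence would estimate the 12-month risk

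*Combined protocol and SAP*

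**What the plan says.** The whole fracture analysis is one sentence in section 11.2.3. Its outcome is "The incidence of rib or vertebral fractures within the treatment field occurring at any time during the entire course of the study (12 months"), which "will be reported and compared between patients receiving placebo or risedronate". It gives no denominator, test, censoring rule or rule for death.

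Other sections determine how long each patient is observed:

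- **Section 7.3:** fracture data "will be collected from standard follow-up CT imaging at 3, 6, 9, and 12 months post SBRT".
- **Section 6.6, footnote f:** "Every 3 month follow-up, and CT imaging will have a window of +/- 8 wks".
- **Section 6.4, minimum:** "Patients will be followed for a minimum of 3 months for assessment of the primary objective".
- **Section 6.4, intention:** "Patients will be ideally followed in total for 12 months after completion of radiation therapy".
- **Section 6.4, withdrawal:** progression or a new cancer that needs chemotherapy ends study follow-up and imaging. Data gathered before that point stay in the analysis, but nothing says how a patient who leaves without a fracture is counted.
- **Sections 3.0 and 3.1:** metastatic lung tumours and ECOG 0 to 3 are eligible, and "Patients must have a life expectancy of at least 3 months as determined by the treating radiation oncologist".

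**The concern.** The endpoint covers 12 months, but the design secures observation for only 3. A patient whose last CT was at 3 months and showed no fracture carries little information about months 4 to 12. In a plain count over all patients, that patient is nevertheless a 12-month non-event. If such patients are left out instead, patients who fractured stay in while some who did not are removed. The resulting rate then depends on an unstated choice of denominator, which could be made after the data are seen.

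Timing adds to this. In the sponsor's own series, described in section 1.1, rib fractures appeared from about 6 months, which is after the guaranteed follow-up ends.

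Fracture is one of the clinical consequences the trial hopes to prevent. At stake are the reported 12-month rate in each arm and, under some conditions, the difference between arms.

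**Working it through.** **Plan's own figures.** The documents give no expected rate, sample size or power for fractures. The only sample size, 42 per group in section 11.4, is for the 3-month cortical thickness endpoint. It reproduces: standardised difference 0.11/0.20 = 0.55, one-sided alpha 0.05 and power 0.80 give 41.57 by two-sample t-test, so 42. The total of 84 in section 3.3 is 2 x 42, with no allowance for loss.

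**Inputs.**

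- True 12-month fracture risk F = 40%, the upper figure quoted in section 1.1.
- Withdrawal by 12 months A = 10% to 50%. This is an assumption; the documents give no rate.
- Constant hazards, with withdrawal independent of fracture. All attrition here is withdrawal, not death.

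**Formulas** (time in years, f = -ln(1-F), a = -ln(1-A)).

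1. All randomised as denominator: C = f/(f+a) x [1 - exp(-(f+a))].
2. Fracture-free leavers dropped: C / [C + (1-F)(1-A)].
3. As 1, but a fracture is seen only if the patient reaches the next scheduled CT: sum over k = 1 to 4 of [exp(-f(k-1)/4) - exp(-fk/4)] x exp(-ak/4).

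Example at A = 40%: f = a = 0.511, so C = 0.5 x (1 - 0.36) = 0.320. Formula 2 gives 0.320/(0.320 + 0.6 x 0.6) = 0.471.

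| Withdrawn (assumed) | All randomised | All randomised, seen only at CT | Fracture-free leavers dropped |
|---|---|---|---|
| 10% | 38.1% | 37.6% | 41.4% |
| 20% | 36.2% | 35.2% | 43.0% |
| 30% | 34.2% | 32.6% | 44.8% |
| 40% | 32.0% | 30.0% | 47.1% |
| 50% | 29.7% | 27.2% | 49.7% |

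The target in every row is 40%. At 40% withdrawal the choice of denominator alone moves the answer from 32% to 47%. If fractures occur only in months 6 to 12 and 30% withdraw, the all-randomised figure is 30.9%.

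**Comparison between arms.** With identical 40% risk, 20% against 40% withdrawal gives 36.2% against 32.0%, a spurious 4.2 points. At 42 per arm this is 0.042 x 42 = 1.8 patients. At an assumed 20% risk the figures are 18.0% and 15.8%, or 2.2 points.

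Rejection rates at a two-sided 5% level, with identical 40% risk (4,000 simulated trials of 42 per arm):

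| Withdrawal by arm | Chi-square on crude proportions | Log-rank |
|---|---|---|
| 30% and 30% | 4.8% | 4.6% |
| 20% and 40% | 7.7% | 5.3% |
| 10% and 50% | 13.2% | 4.7% |

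**Power.** For an assumed 40% against 20%, power with 42 per arm is 0.52 without attrition and 0.44 with 30% withdrawn in both arms. In simulation at 30%, chi-square has 0.448 and log-rank 0.457.

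**Scan timing.** With a window of 8 weeks either way, the 3-month CT can fall at about weeks 5 to 21 (13 ± 8) and the 12-month CT at weeks 44 to 60 (52 ± 8). Time at risk therefore varies even among patients who complete the study.

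**The case against.** Several stronger conclusions are tempting, and the documents do not support them.

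- **That the reported rate will be too low.** This holds only if all randomised patients form the denominator and unseen patients count as fracture-free. Section 11.2.3 does not say so, and dropping fracture-free leavers pushes the rate up. The section names no estimator either; a simple proportion is the natural reading of its wording.
- **That many patients will be lost.** No rate is given. Three months' life expectancy is an entry floor, not a forecast. Section 6.4 also says that immunotherapy, hormonal therapy for breast or prostate cancer, cryoablation and radiofrequency ablation are not reasons for withdrawal.
- **That deaths bias the rate.** If death is a competing event, a patient who dies without a fracture is correctly counted as never fractured. To the extent that attrition is death, the gaps tabulated above shrink.
- **That the comparison between arms is invalid.** One blinded tablet before SBRT gives no obvious reason for arm-dependent withdrawal, and equal independent withdrawal leaves type I error near 5%.
- **That chest wall pain needs the same treatment.** Section 11.2.2 reports pain at each visit and section 7.2 tracks its resolution. A time-to-first-event analysis would discard that.

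It is also fair to say that a time-to-event test recovers almost no power, and that the primary 3-month analysis is untouched by this point.

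What remains is that follow-up is unequal by design and the planned summary does not account for it. Chance imbalance in withdrawal is possible with 42 per arm, and withdrawal for chemotherapy may not be independent of fracture risk.

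**Conclusion.** The point holds in a limited form. As written, section 11.2.3 does not yield an estimate of 12-month fracture risk when patients leave early, and section 6.4 makes early exit part of the design. With a true risk of 40% and 20% to 40% withdrawal, the result is about 4 to 8 points too low or 3 to 7 points too high, depending on the denominator. These sizes rest on assumed withdrawal rates, constant hazards and the highest fracture figure the protocol quotes; at a lower risk they are smaller.

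Bias between arms is conditional: it needs withdrawal that differs by arm or is linked to fracture risk. This is a worthwhile, cheap improvement to a secondary endpoint and does not threaten the trial's main result.

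**What to change.** Rewrite section 11.2.3 as follows:

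1. Estimate the 12-month cumulative incidence of first in-field fracture in all randomised patients, from SBRT, censored at the last evaluable CT, with death before fracture as a competing event.
2. Compare arms with Gray's test and report the 12-month difference with a confidence interval.
3. Use actual scan dates. Because fractures are seen only on CTs about 3 months apart, treat onset as interval-censored in a sensitivity analysis.
4. Report follow-up time and reasons for exit by arm, and add a sensitivity analysis for informative withdrawal due to chemotherapy.

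No new visits or scans are needed. Section 10.0 stores all CT scans and reports, so scan dates should be retrievable. Appendix Q, the fracture form, is not shown in the available text, so whether it records dates should be checked.

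The cost is SAP wording, somewhat more analysis and wider intervals late in follow-up. The gain is a valid 12-month estimate and protection against unequal withdrawal, with little added power.

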2.2 Secondary Objective(s)

- 2.2.1 In addition to the primary objective, we will further analyze the remaining routine follow-up chest CT scans, for mean cortical thickness change in regions of bone that received 0 – 10 Gy, >10 – 20 Gy, > 20 – 30 Gy, > 30 – 40 Gy, and > 40 Gy at all time points including 3 months, 6 months, 9 months, and 12 months. These scans are standard of care and would be performed regardless of inclusion on this trial. This will allow us to determine the potential persistence of effects from SBRT and bisphosphonate use.
- 2.2.2 We will assess and compare the incidence and grade (per modified CTCAE v.5) of radiation induced chest wall pain within the radiation treatment portal (within the 50% isodose line) at time of each routine follow up visit (3 months, 6 months, 9 months, and 12 months post SBRT). The purpose of utilizing a placebo and double-blind design is that chest wall pain is a subjective finding. Furthermore, it is unclear if chest wall pain from radiation is directly due to bone damage, nerve damage, muscle irritation, or a combination of all of these factors. The use of placebo will help us reduce the potential for bias in pain assessment.
- 2.2.3 We will assess and compare the incidence of rib and vertebral fractures (as noted on CT imaging) that occur within 12 months of irradiation and are within the radiation treatment field. The radiation treatment field will be defined as within the 50% isodose line.
- 2.2.4 The urine concentration of an osteoclast-specific biomarker, urinary N-telopeptide (NTX) indicating osteoclast activity will be assessed prior to SBRT and at each routine follow up visit (at 3 months, 6 months, 9 months, and 12 months post SBRT).

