7.4 Urine Biomarkers of Osteoclastic Activity and Bone Turnover

A single urine sample will be collected at baseline and at each follow up point (3,6,9,12 months). Samples will be collected in clinic and immediately transported to the laboratory of [name] on campus for storage in an minus 80 degrees C freezer designed for lab specimen storage. Urinary N-telopeptide (U-NTX) will be measured using ELISA based on an immobilized synthetic peptide with a specific sequence of amino acids matching a section of the N telopeptide (NTX) of type 1 collagen. Samples will be destroyed in biohazard waste immediately after analysis is complete.

The following detailed information on collection and analysis is provided from pacific biomarkers
<https://pacbio.com/ biomarker/assay-detail/148/>

Specimen Type: Urine (2nd morning void preferred; do not add preservative)

Optimum Volume: 1 mL

Stability:

2-8°C	-20°C	-70°C
1 week	3 months	1 year

Reporting units: nM BCE/mmol Cr (normalized)

Method: ELISA

Biological or Clinical Significance:

Bone resorption is a function of osteoclasts. These cells remove the mineral from bone and break down the organic matrix that is primarily comprised of type I collagen. Collagen is a cross-linked fibrous protein that forms the fabric of bone and most other connective tissues. Bone contains three polypeptide chains wound together in a helical structure. The ends of these chains (known as telopeptides) provide the intermolecular cross-linking that gives collagen its strength and resiliency. As these cross-linked domains from bone and other skeletal connective tissues are broken down, the pyridinoline cross-linking domains are released and ultimately excreted into the urine in the form of small peptides bound to pyridinoline (70%) and free pyridinoline (30%). One type of peptide-bound pyridinoline is the cross-linked N-telopeptide (NTX) which is unique to type I bone collagen. NTX can be used to identify fast losers of bone, to monitor therapy, to measure dose response, or to determine patient compliance with therapeutic prescription(s).

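### The urinary NTX analysis (11.2.4) names no risedronate-versus-placebo contrast and gives the collected baseline NTX no role; a baseline-adjusted comparison of arms would be more precise at no cost

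*Combined protocol and SAP*

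**What the plan says.** The NTX analysis in 11.2.4 is two sentences. The first is "The concentration of urinary NTX will be assessed at each time point from baseline to the conclusion of the study at 12 months". The second is "Results will be directly compared in each group". No model, test, effect measure, covariate or named pair of arms follows. Objective 2.2.4 says that the marker "will be assessed prior to SBRT and at each routine follow up visit", and outcome 5.2.4 is no more specific.

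Section 7.4 sets the sampling, "A single urine sample will be collected at baseline and at each follow up point (3,6,9,12 months"), and the scale, "Reporting units: nM BCE/mmol Cr (normalized"). The study calendar (6.6) places urine in the baseline column, apart from the dosing column. Its footnote on the tablet reads "Given once at 7 – 21 days prior to initiation of SBRT".

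Neighbouring sections say more:
- 11.1, 11.2.2 and 11.2.3 name risedronate and placebo as the groups compared.
- 11.2.1 uses percent change from baseline with repeated measures ANOVA.
- 11.3.2 and 11.3.3 give the exploratory urine markers repeated measures models with a group-by-time interaction.

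**The concern.** The trial's hypothesis is that one tablet suppresses early osteoclast activity after SBRT. NTX is the only osteoclast marker in the plan that is both unconditional on funding and measured at every follow-up visit. TRAP5B and other bone-turnover markers are planned at baseline and 6 months, if funding permits (2.3.2, 5.3.2).

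Two things are left open for this marker. The first is the contrast: a comparison within each group describes time trends and does not use the randomisation. The second is the baseline. If follow-up values are compared directly, differences between patients that existed before treatment stay in the error term, although the sample that would remove part of them is already collected. An imprecise result could not separate absence of suppression from failure to detect it. With the method unstated, the choice among follow-up values, change scores and adjustment could also be made after the data are seen.

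**Working it through.** **1. The plan's own figure.** Section 11.4 gives changes of 0.22 and 0.11 mm, an SD of 0.20, one-tailed alpha 0.05 and power 0.80. The standardised difference is (0.22 − 0.11)/0.20 = 0.55. A one-sided two-sample t-test needs 41.6, rounded up to 42 per group, with power 0.80 at 42. The stated 42 reproduces. It concerns cortical thickness and says nothing about power for NTX, so it serves here only as the number of patients per arm.

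**2. Assumptions for NTX.** The documents give no SD, effect size or baseline-to-follow-up correlation (ρ). I assume a difference of 0.5 SD of the follow-up value, ρ from 0.3 to 0.8, equal SDs at baseline and follow-up, one visit, and all 42 per arm contributing.

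**3. Variance of the arm difference, relative to follow-up values alone (= 1).**
- Baseline as covariate: 1 − ρ²
- Unadjusted change from baseline: 2(1 − ρ)

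The second minus the first is 2 − 2ρ − 1 + ρ² = (1 − ρ)², which is never negative. The covariate analysis is therefore never less precise than the change score and, because 1 − ρ² ≤ 1, never less precise than follow-up values alone, apart from the negligible cost of estimating one coefficient.

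**4. Power.** The effective standardised difference is 0.5/√(variance factor), put into a two-sample t-test with 42 per arm. Follow-up values alone give 0.62 (two-sided 5%) or 0.73 (one-sided 5%).

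| ρ (assumed) | 1 − ρ² | Adjusted, two-sided 5% | Unadjusted change, two-sided 5% | Adjusted, one-sided 5% |
|---|---|---|---|---|
| 0.3 | 0.91 | 0.66 | 0.48 | 0.77 |
| 0.5 | 0.75 | 0.74 | 0.62 | 0.84 |
| 0.6 | 0.64 | 0.81 | 0.72 | 0.88 |
| 0.7 | 0.51 | 0.89 | 0.83 | 0.94 |
| 0.8 | 0.36 | 0.97 | 0.95 | 0.98 |

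**5. The same result in patients.** At ρ = 0.5, 42 per arm with adjustment is worth 42/0.75 = 56 per arm without it. At ρ = 0.7 it is worth 42/0.51 = 82. At ρ = 0.3 it is worth only 42/0.91 = 46.

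**6. Attrition.** Section 6.4 withdraws patients who need new systemic chemotherapy, so fewer than 42 per arm will give later samples. That lowers every power figure above.

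**7. Timing of the baseline sample.** Objective 2.2.4 fixes the sample only as before SBRT, and the tablet is taken 7 to 21 days before SBRT. A sample could meet the wording of 2.2.4 and still follow the tablet. Adjusting for such a sample could remove part of the drug effect. The calendar's separate baseline and dosing columns suggest that a pre-tablet sample is intended, but the text does not say so.

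**The case against.** A reader might infer from 11.2.4 that the plan discards the baseline, runs four separate tests, or makes no comparison of arms at all. The documents support none of these. The text is silent on how baseline is used and lists it among the assessed time points, so a change score or a repeated measures model is not excluded. Nor does it mention separate tests by visit. In a two-arm randomised trial whose neighbouring sections compare risedronate with placebo, a comparison of arms is the likeliest intent. The accurate statement is that neither the contrast nor the role of baseline is specified.

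A reader might also take NTX to be the only check of osteoclast suppression, or see a units error in the word concentration. Neither holds. TRAP5B and other markers are in the plan, conditional on funding, and 7.4 already requires normalisation to creatinine. The log scale is a sensible choice for a positive ratio, not the correction of a mistake.

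The effect size and correlations are assumed, and at ρ = 0.3 the gain is small (0.62 to 0.66). Timing also limits what the marker can show. The first post-dose urine is at 3 months, with "Every 3 month follow-up, and CT imaging will have a window of +/- 8 wks", while 6.3 reports that osteoclast activation lasted one week in rodents. A null NTX result could mean that sampling came after the effect had passed, and adjustment cannot repair that.

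These objections narrow the point. They do not remove it: the change-score reading is also never more precise than covariate adjustment, and a likely intent is not a stated contrast.

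**Conclusion.** The point holds as an improvement available at no cost, for a secondary outcome. Section 11.2.4 leaves open both the contrast between arms and the use of a baseline measurement that the trial already takes. Either direct method it could mean is at best as precise as a baseline-adjusted comparison, and less precise at any correlation strictly between 0 and 1. Under the stated assumptions adjustment raises two-sided power from 0.62 to between 0.66 and 0.97, and one-sided power from 0.73 to between 0.77 and 0.98. The direction of the gain follows from the formulas; its size depends on a correlation and an effect size that the documents do not give. The primary analysis and the 42 per group are unaffected.

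**What to change.** Rewrite 11.2.4 as follows:
- State that NTX is compared between risedronate and placebo.
- Use one mixed model for log creatinine-normalised NTX at 3, 6, 9 and 12 months, with arm, visit, arm-by-visit interaction and log baseline NTX/creatinine, allowing for correlation within patients.
- Report the risedronate-to-placebo ratio with its 95% confidence interval at each visit.
- State in 2.2.4, 5.2.4 and 7.4 that the baseline sample used as covariate is taken before the study tablet, so that they agree with the calendar's separate baseline and dosing columns.

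When the result is interpreted, note that the first post-dose sample is at 3 months.

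The cost is a wording change, best made before unblinding. It needs no new samples, visits or patients.
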